## 2.4 Determination of sample size

Due to the pilot character of the study, the sample size is chosen based on both the statistical considerations and practical limitations (eg, to recruit sufficient subjects in a reasonable time to achieve the objectives of the study) and to establish whether a positive trend towards active treatment can be established. For this reason, a one-sided exploratory test is considered appropriate in this setting.

Since no data is currently publicly available on the primary outcome measure in this indication, the sample size is based on assumptions about the likely effect size. Thus, the sample size considerations are only based on assumptions for the effect size index (difference in group means/SD). When the sample size in each group is 15, a 1-sided 5.0% t-test for the comparison of rozanolixizumab and placebo will provide 80% power to detect a statistically significant difference in case there is a large effect of rozanolixizumab with an effect size index of 0.93. In case of a medium index (0.52) the power already decreases to 40%. It will be assumed that 10% of the randomized subjects cannot be utilized for the efficacy analysis; hence 34 subjects will be randomized.

## 3 DATA ANALYSIS CONSIDERATIONS

### 3.1 General presentation of summaries and analyses

Statistical evaluation for the final analyses will be performed by PAREXEL. The Analysis Dataset Model (ADaM) will adhere to Clinical Data Interchange Standards Consortium (CDISC) guidance documents and follow their UCB interpretation.

All analyses will be performed using SAS version 9.4 or higher (SAS Institute, Cary, North Carolina, USA). Continuous variables will be summarized by treatment group (Placebo and rozanolixizumab) and visit (where applicable) with the statistics mean, standard deviation (SD), median, minimum, and maximum. Categorical variables will be summarized by treatment group and visit (where applicable) with frequency counts and percentages. Geometric coefficient of variation (geoCV), geometric mean (geoMean) and 95% Confidence Interval (CI) for the geoMean will also be presented in the descriptive statistics for the PK concentration.

When reporting relative frequencies or other percentage values, the following rules apply:

- For values where all participants fulfill certain criteria, the percentage value will be displayed as 100
- For values where the absolute frequency is zero, there will be no percentage displayed at all
- All other percentage displays will use 1 decimal place
- Percentages displayed based on continuous data (eg, percentage changes from baseline) will be displayed to 1 decimal place.

When reporting descriptive statistics, the following rules will apply in general:

- n will be an integer
- Mean (arithmetic and geometric), SD and median will use 1 decimal place more than the original data
- Coefficient of variation and geoCV will be reported as a percentage to 1 decimal place
- Minimum and maximum will be reported using the same number of decimal places as the original value

---

- If no participants have data at a given timepoint, for example, then only n=0 will be presented. If n<3, then only n, minimum and maximum will be presented. If n=3, then only n, mean, median, minimum and maximum will be presented. The other descriptive statistics will be left blank.

Analyses will be performed by treatment group and for all participants where stated. The treatment groups will be displayed as follows in the TFLs:

- Treatment group 1: Placebo
- Treatment group 2: Rozanolixizumab

Participants with the reduced dose due to tolerability issues will be mapped under the same treatment groups. These participants will be flagged in the listings. For the Observation period the same treatment groups will be displayed.

Data listings containing all documented data and all calculated data, as required for the variables and analysis applicable to the final analyses, will be generated.

The visit type information (home or site visit) will be included into the listings.

### **3.2 General study level definitions**

#### **3.2.1 Analysis time points**

##### **3.2.1.1 Relative day**

Relative day for an event will be derived with the date of the first sc infusion of IMP as reference.

Relative days for an event of measurement occurring before the date of first sc infusion are calculated as follows:

$$\text{Relative Day} = [(\text{Event Date} - \text{Date of First Infusion})]$$

For events or measurements occurring before the date of the first sc infusion, relative day will be prefixed with '-' in the data listings.

The relative day for an event or measurement occurring on or after the reference date to the date of the last infusion is calculated as follows:

$$\text{Relative Day} = [(\text{Event Date} - \text{Date of First Infusion}) + 1]$$

For events or measurements occurring after the date of the last sc infusion, relative day will be prefixed with '+' in the data listings and will be calculated as follows:

$$\text{Relative Day} = + [(\text{Event Date} - \text{Date of Last Infusion})]$$

There is no relative Day 0. Relative day is not calculated for partial dates in cases where relative day is shown in a participant data listing. In such cases, relative day should be presented as '---' in the participant data listings.

#### **3.2.2 Study periods**

The total duration of the study per subject is approximately 28 weeks (up to maximum 40 weeks), consisting of:

- Screening Period of a minimum of 2 to a maximum of 5 weeks starting with Screening Visit (to occur between Day -35 and Day -14, both inclusive).

- Treatment Period (11 weeks) – from first dose of IMP to last dose of IMP. The first treatment with IMP will occur at the Randomization Visit (Visit 2) and the dosing should occur as seamlessly as possible to continue the momentum of the Baseline therapy.
- Observation Period (12 weeks up to 24 weeks) starting day after last IMP dose until study end.

In case of early withdrawal, the duration of the Treatment Period may be shortened depending on the time to withdrawal. The Observation Period may be shortened to 1 week in case a subject completes the Treatment Period and enters the OLE study immediately. In case a subject relapses during the Observation Period, the subject will be stabilized over a period of minimum 2 weeks up to 12 weeks, possibly extending the Observation Period to a maximum of 24 weeks.

The end of the study is defined as the date of the last visit of the last subject in the study.

### 3.3 Definition of Baseline values

Baseline will be the last available pre-dose value prior to the first infusion of study drug in the Treatment Period, or if missing, the Screening values. Assessments with the same date as the first infusion, for which time was not planned to be captured, can be acceptable as Baseline assessments. Scheduled or unscheduled measurements can be used as the Baseline value. Expected measurement-specific Baseline timepoints are presented in [Table 3–1](#). If an unscheduled measurement occurs after the planned baseline measurement timepoint but before dosing, then the unscheduled measurement will be used.

**Table 3–1: Expected Baseline**

Measurement	Definition of Baseline
Safety data: 

• Safety Lab (Clinical chemistry, Hematology, hsCRP, Urinalysis)

• ECG

• Vital signs

• Total protein, albumin, <math>\alpha</math>- and <math>\beta</math>-globulins

	Safety labs, vital signs, total protein, albumin, $\alpha$ - and $\beta$ -globulin: Baseline visit (Day 1), if missing Screening visit. Pre-dose value at Baseline visit will be used for the vital signs.  ECG: mean of triplicate values of Baseline visit. If missing Baseline visit (Day 1), mean of triplicate values of Screening visit.
Efficacy data: 

• iRODS

• INCAT

• Grip strength (assessed by site personnel and patient reported)

• RT-MRC and original MRC

• Fatigue score

• CIDP PRO

• PGIS

• PGIC

	Baseline visit (Day 1), if missing Screening visit  For patient reported grip strength, Baseline value will be defined as the mean of three daily maximum grip strength scores taken by a participant during the last three non-missing days prior to the first IMP. Missing values will be handled as described in Section 4.2.1 .

**Table 3-1: Expected Baseline**

Measurement	Definition of Baseline
Immunological variables: 

• IgA, IgE, IgM

• Serum complement levels (C3, C4),

• Plasma compliment (C3a, C5a)

• [REDACTED]

• Cytokines

• [REDACTED] [REDACTED]

	Baseline visit (Day 1), except for [REDACTED] [REDACTED] where baseline is Screening visit
PD variables: 

• Total serum IgG,

• NF-L levels

	Total serum IgG: Baseline visit (Day 1), if missing Screening visit NF-L: Baseline visit (Day 1)

[REDACTED]; C3= complement component 3; C3a= complement component 3a; C4= complement component 4; C5a= complement component 5a; CIDP= chronic inflammatory demyelinating polyradiculoneuropathy; CIDP PRO=CIDP PRO instrument; ECG= electrocardiogram; IgG= immunoglobulin G; IgA= immunoglobulin A; IgE= immunoglobulin E; IgM= immunoglobulin M; INCAT= Inflammatory Neuropathy Cause and Treatment; iRODS= inflammatory Rasch-built Overall Disability Scale; NF-L= neurofilament light chain; PGIC= Patient Global Impressions of Change; PGIS= Patient Global Impressions of Severity; RT-MRC= Rasch-built, modified-interval Medical Research Council scale.

### **3.4 Protocol deviations**

Important protocol deviations (IPDs) are deviations from the protocol which potentially could have a meaningful impact on study conduct or on the primary efficacy, key safety, or PK/PD outcomes (if applicable) for an individual participant. The criteria for identifying important protocol deviations will be defined in the protocol deviations specifications. Important protocol deviations will be reviewed as part of the ongoing data cleaning process and data evaluation. All important deviations will be identified and documented prior to unblinding to confirm exclusion from analysis sets.

IPDs potentially related to the Coronavirus Disease 2019 (COVID-19) were identified via a specific eCRF page "COVID-19 Impact" per visit with relationship: confirmed, suspected infection, general circumstances around or any other deviation from the protocol due to COVID-19. These deviations will also be reviewed separately as part of the ongoing data cleaning process.

### **3.5 Analysis sets**

The following analysis sets will be defined for this study:

#### **3.5.1 Enrolled Set**

The Enrolled Set (ES) will consist of all participants who have given informed consent.

#### **3.5.2 Randomized Set**

The Randomized Set (RS) will consist of all participants randomized into the study.

#### **3.5.3 Safety Set**

The Safety Set (SS) will consist of all participants, who have received at least one dose of IMP.

Safety variables will be analyzed using the SS.

It is expected that participants will receive treatment as randomized and hence safety analyses will be based on the randomized treatment group. However, if after unblinding it is determined that a participant has received treatment different to the treatment they were randomized to, then for safety analyses the participant will be allocated to the actual treatment they received.

#### **3.5.4 Full Analysis Set**

The Full Analysis Set (FAS) will consist of all participants in the SS, who have a Baseline and at least one valid post-Baseline iRODS measurement up to Visit 17/PEOT (inclusively).

Measurements are considered invalid if the participant received rescue medication before the assessment of iRODS. Assessments collected at the same day as first intake of rescue medication are considered valid. Invalid measurements will not be used for summary tables and MMRM, but kept in listings.

The FAS is the primary analysis set for efficacy analyses. In the case of mistreatment, participants will be analyzed as treated if the participant received the incorrect treatment for the entire study period. In the case of partial mistreatment, patients should be analyzed as randomized, but considered as protocol violators. As for the SS, in the case of mistreatment participants will be primarily analyzed as treated. However, if applicable, sensitivity analyses will also be performed according to the randomized treatment group.

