### **4.2 Handling of dropouts or missing data**

#### **4.2.1 Efficacy data**

For participants who prematurely withdraw for any reason before Week 13 (Day 85), data collected during the PEOT Visit will be used to impute iRODS, INCAT and grip strength at the closest missing visit. In case a participant discontinues the study prematurely, the assessment of the PEOT visit will be mapped to closest missing visit according to the visit schedule utilizing the relative day in study to a maximum of day 85 (Visit 17). However, if a participant receives rescue medication prior to the PEOT visit, the assessment will be regarded invalid and only listed. Assessments on the same day as first intake of rescue medication is acceptable for analysis.

Since the analysis is based on the mixed model repeated measures (MMRM) approach, visits beyond the PEOT Visit will not be imputed. Missing data in-between visits will be covered by the MMRM approach.

For additional analyses of iRODS score to account for missing data, last observation carried forward (LOCF) and multiple imputation will be applied to address the issue of missing scores (see Section 8.1.3). There will be no imputation of missing individual item scores in the summaries for the iRODS; only to the overall iRODS score.

For the analysis of relapse data, participants who withdraw from the study for any reason before Week 13 (Day 85) or who have missing data at Week 13 (Day 85) will be considered as relapsed and analysed as such. The same is true for participants administered an Ig infusion rescue medication during this time interval.

Participants are asked to record three grip strength score assessments at each day. The efficacy parameter will be derived from grip strength scores taken by a participant up to five days prior to the first IMP (for Baseline value) or visit date (for post Baseline visit value):

1. Maximum of grip strength assessments available at a particular day
2. Mean of maximum grip strength over most recent three non-missing days - up to a maximum of five days

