## 8 EFFICACY ANALYSES

All analyses of the efficacy variables will be performed on the FAS. Additional outputs may be repeated for the PPS or the MFAS where indicated. Listings will be based on the SS.

Treatment group assignment for efficacy analysis will be according to the actual treatment regimen.

All efficacy analyses are to be interpreted as exploratory analyses. No p-values will be presented.

Any efficacy measurements are considered invalid, if the participant received rescue medication before the assessment. Assessments collected at the same day as first intake of rescue medication are considered valid. Respective measurements will not be used for summary tables and MMRM, but kept in listings. This includes iRODS, INCAT, clinician reported grip strength, RT-MRC, CIDP PRO and Fatigue, PGIS, PGIC and the patient reported grip strength as derived in Section 8.2.4.

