## 8.2 Statistical analysis of the other efficacy variables

### 8.2.1 CIDP relapse, MMRM and summary tables will be performed on the FAS and repeated for the PPS for iRODS, adjusted INCAT and clinician reported grip strength.CIDP relapse (iRODS)

CIDP relapse (iRODS) is defined as a clinically important deterioration from Baseline in iRODS score, i.e. a standardized change from baseline smaller than or equal to the minimum clinically important differences-standard error (MCID-SE) of  $\leq -1.96$ .

This standardized change from baseline refers to individual person-level responsiveness calculated by individual change divided by their corresponding SE of difference at a given timepoint. [Va15]

$$\text{"MCID - SE"} = \frac{\text{Standardized value}_{\text{Visit}} - \text{Standardized value}_{\text{Baseline}}}{\sqrt{\text{SE}_{\text{Visit}}^2 + \text{SE}_{\text{Baseline}}^2}}$$

Values and changes from Baseline in iRODS scores will be summarized by treatment group and for all participants and listed by treatment group at each scheduled assessment during the Treatment and Observation Period.

The point estimate and the corresponding 2-sided 90% CI for the difference between placebo and rozimab CIDP relapse rates up to week 13 will be reported. The CI will be constructed using the asymptotic standard error (asymptotic Wald confidence limits).

Analyses will be performed for the FAS utilizing the observed cases.

Sensitivity analysis for relapse will be performed in the same way, however for the PPS.

The rule for handling missing data is described in Section 4.2.1.

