### 8.2.9 Use of rescue medication

The percentage of participants with concomitant medication identified as rescue medication [Yes/No] in the eCRF and time to first rescue medication administration will be summarized by treatment group and for all participants and listed by treatment group at each scheduled assessment during the Treatment and Observation Period.

If a participant receives rescue medication at multiple times, the relative day of the first occurrence is used to define the time to rescue medication.

The statistical methods applied to use of rescue medication and time to use of rescue medication will be the same as for CIDP relapse (iRODS), see Sections 8.2.1 and 8.2.1.1. The rule for handling missing data is described in Section 4.2.7.

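### Relapse and rescue are analysed on a set that can drop a dosed participant whom the SAP's own rule counts as relapsed, if no valid post-Baseline iRODS was obtained

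*SAP*

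**What the plan says.** - **Event rule.** SAP 4.2.1 classes as relapsed "participants who withdraw from the study for any reason before Week 13 (Day 85"), those with missing Week 13 data, and those given Ig rescue in that interval. It sets no condition on iRODS data. SAP 8.2.1.1 repeats the rule for withdrawals in the time-to-relapse analysis.
- **Analysis set.** SAP 8: "All analyses of the efficacy variables will be performed on the FAS". SAP 8.2.1 confirms this for relapse: "CIDP relapse, MMRM and summary tables will be performed on the FAS and repeated for the PPS". SAP 8.2.5 does the same for the combined relapse definition. The PPS is a subset of the FAS (SAP 3.5.6).
- **Entry to the FAS.** SAP 3.5.4 requires at least one dose, a Baseline iRODS and "at least one valid post-Baseline iRODS measurement up to Visit 17/PEOT (inclusively"). It adds: "Measurements are considered invalid if the participant received rescue medication before the assessment of iRODS", with one exception: "Assessments collected at the same day as first intake of rescue medication are considered valid".
- **Rescue.** SAP 8.2.9: "The statistical methods applied to use of rescue medication and time to use of rescue medication will be the same" as for iRODS relapse. It names no analysis set, so the general statement in Section 8 applies. For missing data it refers to 4.2.7, not 4.2.1.
- **Elsewhere.** Only the efficacy listings use the Safety Set (SAP 8). The protocol's FAS (14.1.4) already required a post-Baseline iRODS. The rescue-related validity condition came with the SAP.

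**The concern.** The two rules disagree about the same person. SAP 4.2.1 makes a very early withdrawal or rescue a relapse, while SAP 3.5.4 can remove that person from the only sets on which relapse is estimated. They then leave the numerator, the denominator and the Kaplan-Meier curve, and an early rescue also disappears from the rescue endpoint. Inclusion therefore depends partly on the outcome being counted.

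The iRODS condition suits a model of iRODS scores. Rescue use, adjusted INCAT relapse, grip-strength relapse and the investigator-recorded category of relapse in SAP 8.2.5 do not need an iRODS value. In arms of about 17, a single omission is visible in the relapse difference and its interval.

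**Working it through.** **1. The plan's own figures.** SAP 2.4 gives 15 per group, a one-sided 5% t-test and effect sizes of 0.93 and 0.52. With the noncentral t distribution (28 degrees of freedom, noncentrality d×√(15/2)), power is 79.9% and 39.9%, matching the stated 80% and 40%. The 10% allowance gives 30/0.9 = 33.3, rounded up to 34, or 17 per arm at 1:1. These figures reproduce; the point does not rest on an error in them.

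**2. Who is affected.** The first scheduled post-Baseline iRODS is at Visit 4, Day 8 ±2 (protocol Table 5–1 and 9.1; Visits 3, 5 and 7 have none). Applying the rules:

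| Dosed participant | Valid post-Baseline iRODS? | SAP 4.2.1 | In FAS? |
|---|---|---|---|
| Withdraws before Visit 4, no PEOT iRODS | No | Relapsed | No |
| First rescue on a day before any post-Baseline iRODS | No; every later value follows rescue | Relapsed | No |
| Withdraws before Visit 4, PEOT iRODS done with no earlier rescue | Yes | Relapsed | Yes |
| First rescue on the day of the first post-Baseline iRODS | Yes (same-day exception) | Relapsed | Yes |
| Withdraws or is rescued after one valid iRODS | Yes | Relapsed | Yes |

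Only the first two rows conflict.

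**3. Effect on one arm.** Let an arm of 17 have k relapses, one of them dropped:

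k/17 − (k−1)/16 = (16k − 17k + 17)/272 = (17 − k)/272.

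- k = 5: 12/272 = 4.4 points
- k = 9: 8/272 = 2.9 points

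The documents give no relapse rates, so k is assumed.

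**4. Effect on the difference.** SAP 8.2.1 specifies a two-sided 90% Wald interval: p₁ − p₂ ± 1.645×√[p₁(1−p₁)/n₁ + p₂(1−p₂)/n₂]. Assume 5/17 relapses on rozanolixizumab and 9/17 on placebo. The standard error is √(0.294×0.706/17 + 0.529×0.471/17) = 0.164.

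| Relapsers dropped | Rates | Difference, points | 90% CI |
|---|---|---|---|
| None | 5/17 vs 9/17 | −23.5 | −50.5 to +3.4 |
| One on rozanolixizumab | 4/16 vs 9/17 | −27.9 | −54.7 to −1.2 |
| One on placebo | 5/17 vs 8/16 | −20.6 | −48.0 to +6.9 |
| One in each arm | 4/16 vs 8/16 | −25.0 | −52.2 to +2.2 |

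With no true difference (8/17 in each arm), dropping one relapser from one arm creates an apparent difference of 3.3 points (7/16 vs 8/17).

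**5. A related wording conflict.** SAP 8.2.1 also says of the relapse analysis: "Analyses will be performed for the FAS utilizing the observed cases". SAP 4.2.1 assigns an outcome to people whose Week 13 data are not observed. Both cannot govern the same table.

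**The case against.** The strongest reply is that almost nobody should fall in the gap:

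- iRODS is completed before any other assessment at each visit (protocol Table 5–1, note o).
- Early withdrawals should attend a PEOT visit as close as possible to the decision (protocol 8.4), and iRODS is its first assessment.
- Rescue normally follows a relapse judged on scores taken at a visit (protocol 7.7.3), and the same-day value is valid.
- INCAT and site-measured grip strength are scheduled only at visits that also schedule iRODS, so their data would seldom be discarded through the iRODS condition.
- Relapse and rescue are other efficacy variables, all efficacy analyses are exploratory without p-values (SAP 8), and Safety Set listings and the disposition tables would show anyone left out.
- Counting someone with no post-Baseline efficacy data as relapsed is itself an imputation.

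Most of this stands, and it limits the point to a minor one. It does not remove the conflict. PEOT attendance is not assured, and SAP 4.2.1 makes a PEOT value after rescue invalid and only listed. A listing does not correct an estimate. The imputation is one that SAP 4.2.1 has already chosen.

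A reader might infer that early withdrawals and rescues in general are removed. They are not: one valid post-Baseline iRODS keeps the participant in the FAS, counted as relapsed. A reader might also take the 10% allowance in SAP 2.4 as the expected number lost, but it covers all reasons for being unusable and does not estimate these exits.

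**Conclusion.** The inconsistency is real but narrow. It affects only dosed participants with no valid post-Baseline iRODS up to Visit 17/PEOT, in practice mostly exits or rescues in about the first week. For them the relapse analysis contradicts SAP 4.2.1, and a rescue is missing from its own endpoint. No relapse or rescue estimate on a wider set is planned.

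Each such person in an arm of 17 shifts that arm's relapse rate by (17−k)/272, about 3 to 4 points for k between 5 and 9. The values of k and the 5/17 versus 9/17 example are assumptions.

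Three stronger readings are not supported:

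- **A fixed 5.9-point shift per person.** That is 1/17, which the formula gives only at k = 1, when the person dropped is the arm's sole relapse.
- **A probability that someone is lost.** The documents give no rate for lacking a valid iRODS, and the number may be zero.
- **A bias in a known direction.** It depends on which arm loses more people, and equal losses may largely offset.

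The change is worth making because it is cheap, removes an exclusion that depends on the outcome, and leaves results unchanged if nobody is affected.

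**What to change.** In SAP 8.2:

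- Analyse relapse (iRODS, adjusted INCAT, grip strength and any), time to relapse, rescue use and time to rescue on all randomized participants who received at least one dose. State the set in those words: the SAP's Safety Set (3.5.3) no longer requires randomization.
- Apply the 4.2.1 counted-as-relapsed rule to the relapse endpoints only. Count rescue as recorded in the eCRF, so that a withdrawal without rescue does not become a rescue event.
- Reconcile the observed-case sentence in 8.2.1 with 4.2.1.
- Keep the FAS, with its valid-iRODS condition, for the iRODS mixed model.

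The cost is small wording changes in 8.2.1, 8.2.1.1, 8.2.5 and 8.2.9, plus the matching table footnotes. The trade-off is that participants with no post-Baseline efficacy data enter the relapse tables as relapsed, as 4.2.1 already specifies.
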